COVER PAGE

Title of the study: Use of abdominal binder in colonoscopies performed by trainees in Gastrointestinal Endoscopy: A randomized, double-blind, sham-controlled trial

NCT number: NCT05617521

Document date: 01/29/2023

Study Protocol

Introduction

Colonoscopy is widely used for the diagnosis and treatment of colon diseases, and is also the preferred screening test for colorectal cancer (CRC) worldwide.^{1,2} The colonoscopy procedure is safe, well-tolerated, and accurate for examining the mucosa of the entire colon and distal terminal ileum. Nevertheless, it is technically demanding, even for the experienced endoscopists.³ One of the most frequent difficulties is the looping of the sigmoid and transverse colon. Looping stretches the colonic mesentery, leading to pain and discomfort in patients.⁴ Furthermore, looping prolongs the cecal intubation time (CIT), increases the number of incomplete procedures and the risk of associated complications, such as splenic injury and bowel perforation.^{5,6}

Ancillary maneuvers, such as abdominal pressure and patient position change, can be used to avoid the formation of the loops, but their effectiveness is questionable.⁷⁻⁹ The most used is the manual abdominal pressure, usually requiring to be exerted by an assistant, which may result in not effective uncontrolled compression.¹⁰ An abdominal binder is an alternative that seeks to improve the effectiveness of the abdominal pressure, encircling the abdomen to exert the pressure in an uniformly distributed way for the entire duration of the colonoscopy.¹¹

Several randomized controlled trials (RCTs) have evaluated the impact of abdominal compression devices during colonoscopy with contradictory results.¹¹⁻¹⁵ Two meta-analyses have revised these RCTs and both concluded that encircling abdominal devices reduces the CIT, the need for abdominal compression, and the frequency of postural change.^{16,17} Nevertheless, the limitations of both meta-analyses due to the reduced number of RCTs and them heterogeneity are remarkable. In addition, the colonoscopies in all RCTs studies were performed by experienced endoscopists, who would have less trouble managing loops and it would minimize any benefit using the abdominal binder.^{17,18}

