This randomized trial was conducted to evaluate the effectiveness and safety of an abdominal binder use during colonoscopy performed by gastrointestinal endoscopy fellow trainees. We hypothesized that the abdominal binder use would facilitate and increase the effectiveness of the colonoscopy for inexperienced operators.

Methods

Trial design and population

It is a randomized, double-blind, sham-controlled study. The trial was performed at a single-center, Hospital Central Norte PEMEX, a tertiary center with a gastrointestinal endoscopy fellow trainee program with more than 10 years of experience. Outpatients between 20-80 years

scheduled for an elective colonoscopy were prospectively recruited for participation from November 2022 to January 2023. Inclusion criteria were patients with ingestion of the entire bowel preparation and categorized as American Society of Anesthesiologists Class (ASA) \leq III. Exclusion criteria were pregnancy, breastfeeding, multiple planned procedure, previous colorectal resection, history of intraabdominal malignancy, inflammatory bowel disease, liver cirrhosis or ascites, abdominal skin lesions, and anesthesia or analgesic allergy. This trial was conducted in accordance with the most recent version of the Declaration of Helsinki and approved by the local ethical committee. Written informed consent was obtained from all the patients before participation. This manuscript is reported in accordance with CONSORT guidelines.¹⁹ All the authors had reviewed and approved the final manuscript.

Trial interventions and device description

Prior to the procedure, age, sex, height, weight, body mass index (BMI), and colonoscopy indication of all participants were recorded. Once enrolled, patients were randomized to either the abdominal binder (AB) group or the sham binder (SB) group in a 1:1 ratio. Randomization was performed using a web-based computer system (Research Randomizer, Geoffrey C. Urbaniak and Scott Plous) by an independent statistician who had no other intervention in the study. An independent operator printed the randomization number and group for each participant (either the AB or SB group) in individual cards, which were hidden in a locked black box by the same independent operator. Only the nurse, who fitted the abdominal binder to all the patients in a private space, had access to the cards. Randomized data and cards were concealed to study coordinators, endoscopists, clinical staff, and participants.

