Primary outcome of this study was CIT (the time from the scope insertion to intubation of the cecum and visualization of the appendiceal orifice and ileocecal valvule). Main secondary outcomes were the cecal intubation length (CIL), ileocecal valve intubation time (IVIT), manual abdominal compression or postural change requirement, and the need for intervention by the attending endoscopist during the procedure. Other secondary outcomes included colonoscopy completion rate, trainee-reported insertion difficulty, adenoma detection, need for extra analgesic drugs, patient-reported pain, and satisfaction level at discharge of the endoscopy area. Before to leave the recovery room, the patients were asked for pain using a 10-point visual analog scale (VAS), and for satisfaction using a 5-point scale (5= very satisfactory, 4= satisfactory, 3= unsatisfactory, 2= very unsatisfactory, 1= extremely unsatisfactory) by an assistant blinded to the study.

Planned *a priori* subgroup analyses included stratification according to age, gender, and BMI. Participants with incomplete colonoscopy were excluded from the primary outcome analysis (CIT) and two of the main secondary outcomes (CIL and IVIT) yet included for the rest of the secondary outcomes. Primary analysis method was intention-to-treat (ITT), including all randomized participants. A per-protocol (PP) analysis method was also performed, excluding participants in the AB group whose binder was removed or loosened at any time of the procedure.

Bibliography

3. Shahidi N, Ou G, Telford J, Enns R. Establishing the learning curve for achieving competency in

performing colonoscopy: A systematic review. *Gastrointest Endosc* [Internet]. 2014;80(3):410–6. Available from: <http://dx.doi.org/10.1016/j.gie.2014.04.056>

4. Cheng W Bin, Moser MAJ, Kanagaratnam S, Zhang WJ. Analysis of and mathematical model insight into loop formation in colonoscopy. *Proc Inst Mech Eng Part H J Eng Med*. 2012;226(11):858–67.

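### The primary CIT analysis is described as ITT in all randomized participants but leaves out incomplete colonoscopies, and no CIT analysis keeps everyone

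*Protocol*

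**What the plan says.** All the relevant text on analysis populations is in the protocol, Methods, Outcomes.

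- **Definition.** CIT is "the time from the scope insertion to intubation of the cecum and visualization of the appendiceal orifice" and the ileocecal valve, so it exists only when the cecum is reached.
- **Exclusion.** "Participants with incomplete colonoscopy were excluded from the primary outcome analysis (CIT", and from CIL and IVIT. These participants stay in for the other secondary outcomes.
- **Label.** The following sentence reads "Primary analysis method was intention-to-treat (ITT), including all randomized participants".
- **Per-protocol set.** It is formed by "excluding participants in the AB group whose binder was removed or loosened at any time of the procedure". Completion plays no part in it.
- **Related outcomes.** "Other secondary outcomes included colonoscopy completion rate", and the main secondary outcomes include "the need for intervention by the attending endoscopist during the procedure".

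The SAP sizes the trial for CIT at 142 participants (60 s difference, SD 110 s, 90% power, two-sided alpha 0.05) and includes 206. It plans a t test or a Mann-Whitney test according to normality. It defines no analysis set, no handling of participants without a CIT, and no sensitivity analysis.

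**The concern.** Two adjacent sentences cannot both hold for the primary outcome once a single colonoscopy is incomplete. The plan clearly expects some: it writes a rule for them and lists completion as an outcome.

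The issue goes beyond wording because completion happens after randomization and may depend on treatment. The protocol's Introduction says that "looping prolongs the cecal intubation time (CIT), increases the number of incomplete procedures". Looping is what the binder is meant to reduce. The participants removed from the CIT comparison may therefore be mostly slow ones, removed at different rates in the two arms. The direction of any bias would depend on the binder's effect on completion:

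- If it helps completion, more slow cases drop out of the sham arm and the benefit in CIT is understated.
- If it hinders completion, the benefit is overstated.

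A reader told that the analysis is ITT would not look for either.

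**Working it through.** **1. The plan's own figure.** Inputs from the SAP: difference 60 s, SD 110 s, two-sided alpha 0.05, power 90%.

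n per arm = 2 × (1.960 + 1.282)² × (110/60)² = 70.6, rounded up to 71, so 142 in total. This reproduces the SAP.

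**2. Precision is not the problem.** 206 − 142 = 64, and 64/206 = 31%. Nearly a third could be lost before the number analysed fell below the SAP's requirement.

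**3. Bias from selection.** Assumptions: normal CIT, SD 110 s, true benefit 60 s, 103 per arm. A procedure fails when a latent score, with correlation ρ to CIT, exceeds the arm's threshold. The documents give no failure rate, so all rates below are assumed. With φ the standard normal density and z the standard normal quantile:

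L(p) = φ(z₁₋ₚ)/(1 − p)

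completers-only difference = 60 + 110 × ρ × [L(p_binder) − L(p_sham)]

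*Common limit.* The sham rate fixes a cut-off. The binder rate is the upper tail beyond z₁₋ₚ + 60/110. The ρ = 0.5 column uses the same pair of rates. At ρ = 0 every row gives 60 s.

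| Sham fail | Binder fail | ρ = 0.5 | ρ = 1 | t-test power at ρ = 1 |
|---|---|---|---|---|
| 2% | 0.5% | 58.0 s | 56.1 s | 96.4% |
| 5% | 1.4% | 56.1 s | 52.1 s | 94.7% |
| 10% | 3.4% | 53.6 s | 47.1 s | 91.5% |
| 20% | 8.3% | 49.9 s | 39.8 s | 82.9% |

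Example, 10% row at ρ = 1: 60 + 110 × (0.0778 − 0.1950) = 60 − 12.9 = 47.1 s. Power is from 10,000 simulated trials per row.

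*Fixed unequal rates.* L(0.15) = 0.2743 and L(0.05) = 0.1086, so 110 × 0.1657 = 18.2 s.

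| Sham / binder fail | ρ = 0 | ρ = 0.5 | ρ = 1 |
|---|---|---|---|
| 15% / 5% | 60.0 s | 50.9 s | 41.8 s |
| 5% / 15% | 60.0 s | 69.1 s | 78.2 s |

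**4. False positives on time.** With no effect on time and equal failure of 5%, 10% or 20%, the completers-only t test rejects 4.8% to 5.2% of the time. With 15% against 5% failure and still no effect on time, it rejects about 5% at ρ = 0, 8% to 9% at ρ = 0.5 and about 26% at ρ = 1.

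**5. An all-randomized alternative.** This is a Mann-Whitney test with incompletes ranked worst, again simulated with 10,000 trials per scenario.

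- Under the common limit at ρ = 1, its power is 96.4% to 96.8%.
- With equal failure unrelated to speed at 5/10/15/20%, its power is 92.5/86.5/77.0/67.6%, against 96.8/96.0/94.7/93.6% for completers only.
- With failure unrelated to speed, 5% sham and 15% binder, its power is 42.8%. The completers-only test is then unbiased, with 95.8%.
- With no effect on time and 15% against 5% failure in either direction, it rejects about 24% of the time, because it also responds to completion.

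**The case against.** The strongest reply is that nothing is hidden. The exclusion is stated by outcome immediately before the ITT sentence, so the pair can be read as an exception followed by a general rule. CIT cannot be measured without cecal intubation. Completion is already a listed outcome, compared by the SAP's categorical tests. All this is true and makes the completers-only estimate legitimate. It does not make the label right, because the sentence specifies all randomized participants and so goes further than analysis as allocated.

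A second reply is that the larger biases need generous assumptions. The SAP's only loss allowance is its 10% expansion, which is not an incompletion rate. With sham failure up to 10% under a common limit, the difference stays at 47 s or more and power at about 92%, above the 90% target. If the binder works as hypothesized, the bias is toward the null. Bias in its favour requires that it hinder completion, which no passage suggests. The calculations also assume normal times, while the SAP allows for non-normal data. These points stand and limit the severity.

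A third reply is that the worst-rank test is a composite, so disagreement with the main result would not separate bias from a difference in completion. That also stands. It is the reason for using the test only as a sensitivity analysis, read beside the completion table.

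**Conclusion.** The concern holds. The ITT description is wrong as written for CIT, CIL and IVIT if any colonoscopy was incomplete, and neither the per-protocol definition nor the SAP repairs it. That part is certain.

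The effect on the estimate is conditional. It requires failures to be disproportionately slow and their frequency to differ by arm. The link between looping, time and incompletion rests on one general sentence in the Introduction. The documents give no incompletion rate, causes or time limit. Across the assumed scenarios a true 60 s benefit could appear as anything from about 40 s to 78 s, or as exactly 60 s when failure is unrelated to speed. If incompletes are few and balanced, the numerical effect is small. Severity is minor to moderate: worth correcting, but not a reason to discard the CIT result.

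**What to change.** 1. Label the CIT, CIL and IVIT results as completers only, analysed as allocated, not ITT. Keep the ITT label for outcomes that include all randomized participants.
2. Beside those results, report the number of incomplete procedures by arm and cause.
3. State how a procedure finished by the attending endoscopist was counted for CIT and for completion. The documents do not say.
4. Add one all-randomized sensitivity analysis for CIT and IVIT: Mann-Whitney with incompletes ranked worst, described as a composite of completion and time.
5. Date that addition, and disclose it as post hoc if outcome data had been seen. Patients were "prospectively recruited for participation from November 2022 to January 2023", and the SAP is dated 09/24/2023.
6. Keep the completers-only difference in seconds as the main CIT estimate.

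The cost is a relabel, a table and one extra test per outcome on data already held, with no new patients. The sensitivity analysis is not in seconds, mixes completion with speed and can lose much power, so it should accompany the completers-only estimate and not replace it.

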The abdominal binder used for the patients allocated in the AB group was the Revive 3-in-1 Postpartum Recovery Support Belt (KeaBabies® Co., CA, USA). Its price is \$29.96. The device is manufactured in two size, One Size and X-Large. For the patients with a waist circumference >110 cm it was used the X-Large model. The three belts that make up the binder were fitted to all the participants. Once placed, the binder was adjusted to be located between the subcostal border and the anterior superior iliac spine. The participants were asked to confirm that the binder was fastened tightly but not uncomfortably. For the participants in the SB group the same binder was fitted, but once the patient was sedated, it was loosened by the same nurse. The participants wore a non-transparent gown over the binder so that it was not visible to the endoscopists.

Colonoscopy procedure details

Bowel preparation with 4 L of polyethylene glycol solution in split-dose (2 L at the afternoon of the day before and 5 h before the colonoscopy) was used in all the participants.²⁰ In this trial, all colonoscopy procedure were performed by two second-year fellow trainees in gastrointestinal endoscopy with 32 and 38 registered colonoscopies previous to the study.

A standard video-colonoscope (EC-3890Li, PENTAX Co., Tokyo, Japan) was used. All the patients were placed in the left lateral decubitus position. Sedation with propofol and fentanyl was initially performed in most cases, adding dexmedetomidine in one case. Then, the colonoscopy was started using standard maneuvers. Manual abdominal compression and postural change were conducted by a technician when required by the endoscopy trainee or the attending endoscopist. Endoscopist or anesthesiology were allowed to remove the binder at any time during the procedure if they resolve it was necessary for safety. Air insufflation was used during colonoscopy.

Outcomes

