Statistical Analysis Plan

Use of abdominal binder in colonoscopies performed by trainees in
Gastrointestinal Endoscopy: A randomized, double-blind, sham-
controlled trial

NCT05617521

09/24/2023

Sample size was estimated over the primary outcome of the study based on pre-experimental data estimation and previously reported CIT and SD of similar studies with fellows' participation. It was calculated that 142 participants were needed to detect a 60-second difference in CIT (SD 110 sec), with 90% power and two-side alpha 0.05. Moreover, it was also calculated based on the frequency of ancillary maneuvers, using pre-experimental data estimation and literature data. It was found that 186 participants (93 per group) were needed to detect a 20% reduction in the use of ancillary maneuvers, with 90% power and two-side alpha 0.05. As a preventive measure in case of withdrawal or exclusion, the sample was expanded by 10%, a total of 206 patients, 103 in each group were included in the study.

Descriptive statistical analysis, including mean, mode, and frequencies will be performed for the description of the study data. The comparative analysis of the quantitative data will be previously subjected to normality evaluation by the Shapiro–Wilk test and graphical analyses. According to the normality, data comparative analysis will be performed either with a two-way Student's test or U Mann–Whitney test. For the comparative analyses of the categorical data (e.g., manual abdominal compression, postural change, need of intervention by the attending endoscopist) will be used chi-square or Fisher' exact test. A p value of <0.05 will be accepted as statistical significance. Statistical inferential analysis will be performed using RStudio® (R Core Team v.1.2.5033; R Foundation for Statistical Computing, Vienna, Austria) and SPSS® Statistics for Windows Version 23.0 (IBM Corp., Armonk, NY, USA). RStudio® (R Core Team v.1.2.5033) will be also used for drawing graphics. The study biostatistician (SA) will be blinded to the randomization phase and recollection data process.

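### Does the plan leave open whether an insertion finished by the attending counts towards cecal intubation time?

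*Protocol*

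**What the plan says.** All of the following is in the protocol's Methods unless stated.

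- **Primary outcome (Outcomes).** CIT is "the time from the scope insertion to intubation of the cecum and visualization of the appendiceal orifice" and the ileocecal valve. No operator is named.
- **Exclusion (Outcomes).** "Participants with incomplete colonoscopy were excluded from the primary outcome analysis (CIT) and two of the main secondary outcomes (CIL and IVIT"). These participants remain in the other secondary analyses. CIL is cecal intubation length and IVIT is ileocecal valve intubation time.
- **Related outcomes (Outcomes).** The main secondary outcomes include "the need for intervention by the attending endoscopist during the procedure". Completion comes in a separate, lower tier: "Other secondary outcomes included colonoscopy completion rate".
- **Analysis populations (Outcomes).** "Primary analysis method was intention-to-treat (ITT), including all randomized participants". The per-protocol analysis drops only binder-arm participants whose binder was taken off or loosened.
- **Operators (Colonoscopy procedure details).** "all colonoscopy procedure were performed by two second-year fellow trainees in gastrointestinal endoscopy".
- **SAP.** Attending intervention appears only as an example of a categorical outcome for a chi-square or Fisher test. The sample size paragraph states that "142 participants were needed to detect a 60-second difference in CIT (SD 110 sec"), at 90% power and two-sided alpha 0.05. The total was set at 206, or 103 per arm.

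**The concern.** In a trainee study, some insertions may be started by the trainee and finished by the attending. The plan expects attending intervention, since it is a main secondary outcome, yet gives no explicit rule for CIT in such cases. Two classifications can be imagined. The case counts, because the cecum was reached. Or it is incomplete, because the trainee did not get there and the protocol describes the trainees as performing every procedure.

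The difference would matter. Keeping the cases gives a comparison by randomised arm of the time to reach the cecum under supervised trainee practice. Dropping them removes patients after randomisation for an event that the binder might itself influence, so the remaining groups need not be comparable. CIT, CIL, IVIT and the completion-rate numerator would all be affected. The intention-to-treat sentence does not settle it, because the same paragraph carves incomplete cases out of CIT. Timing adds to the worry. Patients were "prospectively recruited for participation from November 2022 to January 2023", and the SAP, dated 09/24/2023, came about eight months later and is still silent.

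**Working it through.** **1. The plan's own figure.** Inputs from the SAP: difference 60 s, SD 110 s, 90% power, two-sided alpha 0.05, 1:1 allocation. Per arm, n = 2 × (1.960 + 1.282)² × (110/60)² = 70.7, so 71 per arm and 142 in total. This agrees with the SAP.

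**2. What the text supports.**

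- The CIT definition has a start (scope insertion) and an end (cecum reached, landmarks seen). An attending-finished insertion has both.
- The Introduction names incomplete procedures as a consequence of looping, with no reference to who held the scope. The term describes the procedure.
- Attending intervention and completion rate are listed as distinct outcomes. If every takeover made a colonoscopy incomplete, the two would largely duplicate each other.
- The documents state two grounds for leaving a randomised participant out of an analysis: incomplete colonoscopy (for CIT, CIL and IVIT) and a removed or loosened binder (per-protocol). Attending intervention is neither.
- The sentence about the two trainees describes operators and their experience. It is not an analysis rule and, taken literally, would leave no attending-finished insertions to classify.
- The procedure section has the attending asking for manual compression or a change of position. Neither document says that the attending advanced the scope.

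Excluding attending-finished cases would need a rule that neither document contains.

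**3. Numbers lost, if takeovers were excluded equally in both arms.** With 103 per arm, a 60 s difference and SD 110 s, power is 97.5% with none excluded, 96.0% at 10%, 93.8% at 20% and 90.6% at 30%. Since 206 − 142 = 64 and 64/206 = 31%, the planned 90% holds up to about that share.

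**4. Bias, if takeovers were excluded and unequal.** The takeover rates and the link with CIT are assumptions. Suppose that within each arm CIT and a latent tendency to takeover are bivariate normal with correlation ρ, and that takeover occurs above a threshold common to both arms. SB is the sham arm and AB the binder arm. With L(p) = φ(z₁₋ₚ)/(1 − p), the difference among the remaining patients is

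60 − ρ × 110 × [L(p_SB) − L(p_AB)] seconds.

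*Model A: the binder lowers the takeover tendency by 60/110 = 0.545 SD whatever ρ is.* For p_SB = 20%, z = 0.842, so p_AB = 1 − Φ(0.842 + 0.545) = 8.3%. Then L(0.200) = 0.350 and L(0.083) = 0.166. At ρ = 1 the difference is 60 − 110 × 0.184 = 39.8 s.

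| Takeover SB / AB | ρ = 1 | ρ = 0.5 | ρ = 0 | ρ = −0.5 |
|---|---|---|---|---|
| 5.0% / 1.4% | 52.1 | 56.1 | 60.0 | 63.9 |
| 10.0% / 3.4% | 47.1 | 53.6 | 60.0 | 66.4 |
| 20.0% / 8.3% | 39.8 | 49.9 | 60.0 | 70.1 |
| 30.0% / 14.2% | 34.2 | 47.1 | 60.0 | 72.9 |

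Simulated power at ρ = 1 for 10, 20 and 30% sham takeover is 92, 84 and 72%. With all cases counted it is about 97%.

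*Model B: the binder affects takeover only through CIT.* The shift is then ρ × 0.545 SD. For p_SB = 20%:

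- ρ = 0.5: p_AB = 1 − Φ(0.842 + 0.273) = 13.3%, L = 0.247, difference 60 − 55 × 0.103 = 54.3 s.
- ρ = −0.5: p_AB = 1 − Φ(0.842 − 0.273) = 28.5%, L = 0.474, difference 60 + 55 × (0.350 − 0.474) = 53.2 s.
- ρ = 1 and ρ = 0 give 39.8 and 60 s, as in model A.

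For p_SB = 30% the four values (ρ = 1, 0.5, 0, −0.5) are 34.2, 53.0, 60 and 51.9 s. None exceeds 60 s.

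The increases in the last column of the table therefore need two things together: faster insertions being the ones taken over, and a binder effect on takeover separate from its effect on CIT.

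**The case for a change.** The strongest reply is that a natural reading is not a written one. The hypothesis is about inexperienced operators, so an analyst could in good faith regard a case rescued by the attending as a failed trainee insertion and set it aside. The key terms have no formal definition, and a SAP finalised after recruitment was the obvious place to settle them. Comparing intervention rates by arm would show an imbalance, but not which patients entered the CIT analysis. A definition would cost only a few sentences.

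Part of this stands. Incomplete, completion and intervention are undefined, and a reader of the results would want to know which cases were counted. If attending-finished cases were in fact left out, the report should say so and give their number by arm.

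The rest does not show a plan that goes wrong. The exclusionary reading depends on inference from the hypothesis and from a description of the operators. The proposed remedy writes down the reading that the text already favours and requires no different analysis. A definition added to the SAP now could not serve as prespecification either; what helps a reader is disclosure of what was done. Counting all operators' time does mix trainee and attending performance, but that is a fair trade for keeping the randomised groups whole.

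**Conclusion.** The concern identifies missing detail, not a rule that gives a wrong answer. The better-supported reading is operator-neutral: incomplete means the cecum was not reached, and an insertion the attending finishes remains in CIT. On that reading the 60 s target and about 97% power with 103 per arm are untouched, taking the SAP's difference and SD to describe CIT whoever held the scope.

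Harm arises only if the opposite was done and takeovers were common, unequal between arms and related to CIT. None of these conditions can be checked from the documents. If slow insertions were the ones taken over, the effect is dilution: at 20% sham takeover, 39.8 s at a correlation of 1 and 49.9 to 54.3 s at 0.5, depending on how the binder acts. Inflation needs a negative correlation plus a separate binder effect on takeover. At 5% sham takeover the shift is at most about 8 s.

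No change to the plan is called for. One sentence in the report on how these cases were counted would be enough. This does not address the separate question of how the exclusion of procedures that never reached the cecum fits with the intention-to-treat statement.

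### The per-protocol rule counts binder releases over the whole procedure, although cecal intubation time ends at the cecum

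*Protocol*

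**What the plan says.** All of the PP text is in the Protocol, Methods, Outcomes.

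- **Primary outcome.** CIT is defined as "the time from the scope insertion to intubation of the cecum and visualization of the appendiceal orifice and ileocecal valvule".
- **PP rule.** The PP analysis is run by "excluding participants in the AB group whose binder was removed or loosened at any time of the procedure". No separate PP set is defined for insertion outcomes.
- **Status of PP.** "Primary analysis method was intention-to-treat (ITT), including all randomized participants". PP is additional.
- **Other outcomes.** "Main secondary outcomes were the cecal intubation length (CIL), ileocecal valve intubation time (IVIT), manual abdominal compression or postural change requirement", along with the need for the attending endoscopist to intervene. CIL and IVIT (ileocecal valve intubation time) are named, but their endpoints are not defined. Other secondary outcomes reach past the cecum: "adenoma detection, need for extra analgesic drugs, patient-reported pain, and satisfaction level at discharge of the endoscopy area".

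Under Colonoscopy procedure details, the Protocol says: "Endoscopist or anesthesiology were allowed to remove the binder at any time during the procedure if they resolve it was necessary for safety". The Introduction describes a binder as meant to "exert the pressure in an uniformly distributed way for the entire duration of the colonoscopy".

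The SAP does not mention a PP analysis, so it neither narrows nor clarifies the rule.

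**The concern.** The outcome and the exclusion rule cover different periods. CIT is fixed once the cecum is reached and its landmarks are seen. The procedure continues after that, and adenoma detection is itself a listed outcome. Removal is permitted throughout, so a release after the cecum is foreseeable under the Protocol's own terms.

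For CIT, a patient released only after the cecum received the assigned compression over the entire period measured. The rule nevertheless treats that patient as non-adherent, so an event after the endpoint decides who enters the analysis of that endpoint. The filter applies to AB only, so any resulting change in the AB mean passes in full into the PP difference between groups. If late releases went with long or difficult procedures, slow AB insertions would be dropped and PP CIT would flatter the binder. If they went with quick insertions, the change would run the other way. In either case, usable adherent data are discarded.

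**Working it through.** **1. The plan's own figure.** SAP, sample size paragraph: difference 60 s, SD 110 s, 90% power, two-sided alpha 0.05, total 142. The allocation is 1:1 (Protocol, Trial interventions).

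n per group = 2 × (1.960 + 1.282)² × 110² / 60² ≈ 70.6, rounded up to 71; 2 × 71 = 142.

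The figure reproduces exactly. It does not depend on the PP rule, so this point leaves it unchanged.

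**2. The two windows side by side.**

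| Binder released (AB) | Compressed for all of CIT? | In PP CIT as written? |
|---|---|---|
| Never | Yes | Yes |
| Before the cecum | No | No |
| Only after the cecum | Yes | No |

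The third row is the mismatch. CIL very probably behaves in the same way, since its name ties it to the cecum, but its endpoint is not stated. IVIT may end later than CIT and needs its own cut-off.

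**3. Possible shift in the PP AB mean.** The SAP gives 103 patients per group. The calculation takes all 103 as having a CIT value, although incomplete colonoscopies are in fact excluded from that outcome. Two inputs are not in the documents and are assumed:

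- k = number of AB patients released only after the cecum
- d = their mean CIT minus the mean of all 103 AB patients

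Dropping them lowers the AB mean by k × d / (103 − k). With d = 110 s, one SD in the SAP:

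- k = 0: 0 s
- k = 2: 2 × 110 / 101 = 2.2 s
- k = 5: 5 × 110 / 98 = 5.6 s
- k = 10: 10 × 110 / 93 = 11.8 s, or 11.8 / 60 ≈ 20% of the target difference

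If d = 0 the shift is zero, and if d is negative the sign reverses.

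The same quantity can be written as the dropped share times D, where D is the difference between dropped and retained patients. This gives 2% × 60 s = 1.2 s, 5% × 110 s = 5.5 s, 10% × 110 s = 11 s and 10% × 220 s = 22 s.

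**4. Cost in precision.** Power for a 60 s difference (SD 110 s), with 103 in the sham group and 103 − k in AB:

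| k | 0 | 5 | 10 | 20 | 40 |
|---|---|---|---|---|---|
| Power | 0.975 | 0.972 | 0.968 | 0.959 | 0.927 |

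Lost precision is therefore not the issue. What matters is who is selected into the analysis.

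**The case against.** The strongest case for leaving the rule alone has five parts.

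- **No late release is documented.** Removal is permitted only for safety, and the documents give no count or timing of releases. A reader might infer that adherent patients were in fact wrongly dropped from PP CIT. The documents do not support that; they show only that the rule would drop such a patient. This part stands.
- **The direction of any bias is conjecture.** A reader might infer that the PP result is tilted towards the binder. That needs late release to go with slow insertion, which nothing in the documents establishes. The value of 110 s for d is an illustration. The SAP also allows a Mann–Whitney test, for which a shift in means would not describe the result directly. This part stands too.
- **Only a supplementary analysis is affected.** This is correct. A reader might infer that the primary CIT conclusion is at risk, but intention-to-treat is the stated primary method and is untouched.
- **One whole-procedure PP set suits the device.** The Introduction describes compression for the full colonoscopy, several outcomes extend past the cecum, and a common set keeps one denominator. This carries less weight. The Introduction is a general description of binders and does not define adherence for CIT. The Outcomes section already varies its analysis sets by outcome, since incomplete colonoscopies are left out of CIT, CIL and IVIT but kept for the rest.
- **New data collection is too late.** Recruitment is reported as November 2022 to January 2023, and the SAP is dated 09/24/2023. This stands and limits the remedy to existing records.

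**Conclusion.** The concern holds in a limited, conditional form. As written, the PP rule lets an event after the endpoint decide who enters the PP analysis of CIT and, by reasonable inference, CIL. Nothing in the SAP corrects this.

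The effect is confined to the supplementary PP analysis. It is zero if no AB binder was released after the cecum, or if those released late had the same mean CIT as the rest. Otherwise its size and direction cannot be known from the documents. The illustration of about 2 to 12 s rests on 2 to 10 late releases among 103 AB patients and on a mean 110 s above the AB average; both are assumptions.

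Releases during insertion are a separate matter: they may be related to difficulty and are excluded from the AB group only. This point does not address that, and correcting the window would not make PP CIT free of selection. Severity: minor.

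**What to change.** Amend the PP definition so that the window ends at the endpoint of each insertion outcome:

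- **CIT and CIL:** exclude an AB participant only if the binder was removed or loosened before cecal intubation.
- **IVIT:** exclude only if this happened before ileocecal valve intubation.
- **Whole-procedure outcomes:** keep the present rule.

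State the endpoints of CIL and IVIT in the same place, and carry the PP definition into the SAP.

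Report the number of AB releases before and after the cecum from existing records. Because the Protocol describes the PP analysis as already performed, label the revised PP CIT result as a later refinement and show it beside the result under the present rule. If release timing was not recorded, state that as a limitation of the PP CIT result.

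The cost is about one sentence in the PP definition, a check of the procedure records, and one re-run of the PP analysis for three outcomes. The small downside is that PP denominators will differ slightly between outcomes. The intention-to-treat analysis and the sample size need no change.
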